### 5.3 Description of Evaluations

This research utilizes validated methods for evaluating the clinical impact of the device/treatment, including several identified in the FDA guidance document regarding clinical studies that investigate urinary incontinence. Stress urinary incontinence episodes per day data, obtained from the subject's Daily Log, serves as the primary efficacy outcome measure (see 2.2). Analysis of adverse events serves as the primary safety outcome measure (see 2.2). Evaluations utilized throughout the study are described below. See 9.5 for detail regarding strategies for analyzing the data obtained in these evaluations.

- I-QoL Questionnaire (Pre- and Post-study) the Incontinence Quality of Life (I-QoL) questionnaire is validated tool for assessing changes in the degree to which urinary incontinence affects a woman's quality of life (TR-1131-FORM-2). It comprises 22 questions, to which the subject provides a numeric response on a 1-5 scale. The score is the sum of the numeric responses, which can range from 22 to 110. A change of 2.5 points is considered clinically significant. The I-QoL questionnaire is provided to the subjects as part of pre- and post-study materials. Completed questionnaires are returned to Elidah via mail or electronically (see 10.4).
- 24-Hour Pad Weight Test (Pre- and Post-study) This test is used to quantify the volume of urine leakage. The subject wears an absorbent pad(s) over a period of 24 hours, after which the pad(s) are weighed to determine the mass of any leaked urine. A reduction of ≥50% compared to a baseline measure is considered clinically significant. A mass of less than 1.3g is considered to be "dry", i.e. no leakage. Pre-weighed pads will be sent to the subjects as part of the study materials. During pre- and post-study assessments the subjects will wear the pad(s) for 24 hours, seal the pad(s) in a moisture proof bag, and mail to Elidah for weighing. Note that although this assessment does provide an objective

measure of change in leakage volume, the method is known to be subject to variability, may not be meaningful to patients, and requires subject compliance. For this reason, Elidah has identified this tool as a secondary outcome measure and does not intend to use the data as a primary means for establishing device efficacy.

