## 9. STATISTICAL CONSIDERATIONS

#### 9.1 Sample Size and Power Analysis

The study is designed to test the null hypothesis that the treatment group and control group are not different (see 2.3). Specific reference is made to the number of subjects who achieve a  $\geq$ 50% reduction in stress urinary incontinence episodes per day when comparing the final outcome to a baseline measure. Several comparable studies were identified in the literature in which similar " $\geq$ 50% reduction in episodes" metrics were reported. From these, sample-size calculations were performed to provide confidence that sufficient subjects would be enrolled to protect against Type II error. Each of these calculations target 80% power and assume an alpha of 2.5%, a 2:1 treatment to control randomization ratio, and a single-tailed test.

• From Sand *et al*, 48% of subjects in the active group (2 treatments per day) were responders compared to 13% of subjects in a control (sham) group. Using these values in a chi-squared sample size calculation one finds that the treatment group for the proposed study needs to enroll 31 subjects.

<sup>1 Sand et al, "Pelvic floor electrical stimulation in the treatment of genuine stress incontinence: A multi-center, placebocontrolled trial", Am J Obstet Cycecol, 173(1):72-79, July 1995.

- From Richardson *et al*, 62% and 73% of subjects (1 treatment/day and 1 treatment every other day) were responders. This study makes reference to the response rate for the sham group in the Sand et al study (13%). Using the 62% and 13% values in a chi-squared sample size calculation one finds that the treatment group for the proposed study should include 16 subjects.
- From a similar, ongoing study in which Elidah is also the Investigator (WIRB-20162650), to date, 71% of subjects are responders. Conservatively estimating the control responder rate at 15% (about the average rate reported in the AHRQ meta-analysis for the control groups in studies using vaginal EMS, Table F97), using a chi-squared sample size calculation one finds that the treatment group for the proposed study needs to enroll 12 subjects.

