with a total alpha of 0.05 will be used to address multiple endpoint related multiplicity problems. These secondary outcome measures are only intended to be analyzed if the primary efficacy endpoint is met. Accordingly, no Type 1 error rate multiplicity adjustment is retrospectively applied to the primary endpoint. The three test are:

- **24h Pad Weight** Subjects with pad weight reductions of ≥50% (i.e. clinically significant) will be considered responders and the groups will be compared using the Fisher's exact test in a similar manner to the analysis of the primary outcome measure.
- **I-QoL** Quality of life scores will be analyzed with respect to a change from baseline. Responders will be those with an I-QoL score increase of 2.5 points, which is defined in the FDA guidance as clinically significant. Treatment and control groups will be compared using the Fisher's exact test.
- **Pad Use** As with the 24h pad weight test, reduction in pad usage will be assessed with respect to a reduction in the number of pads used per day and a 50% reduction will be considered clinically significant. Subjects who do not use a pad during the baseline week will be excluded from the analysis.

Other analyses that may be made but which are not prospectively included within the group of three formal secondary outcome measures (and therefore are not considered with respect to multiplicity adjustments) include:

- Alternate analysis methods for the 24h Pad Weight, I-QoL and Pad Use test will be performed. For each, the mass/score/number data can analyzed using a paired sample ttest to determine whether there is a mean difference between the groups. Further, for the 24h Pad Weight test, a "cure" rate may also be calculated wherein a cure is defined in terms of dryness, which the FDA guidance document recommends defining as a pad weight increase of less than 1.3 grams.
- Usability surveys will solicit subject feedback pertaining to their experience with the product. Appropriate statistical methods will be used in reporting these subjective measures. For example, the Fisher's exact test may be used to determine whether a significant difference exists in responses to the question "Are you satisfied with the treatment"

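### The formal I-QoL test compares responder proportions and leaves the score analyses informal, which gives up power in a test meant to support labelling.

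*Combined protocol and SAP*

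**What the plan says.** **The score (Section 5.3).** The questionnaire has 22 items, each answered from 1 to 5, and they are added up: "The score is the sum of the numeric responses, which can range from 22 to 110". On the threshold, the same section says: "A change of 2.5 points is considered clinically significant", which the plan attributes to FDA guidance.

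**The formal test (Section 9.5).** "Responders will be those with an I-QoL score increase of 2.5 points", and then "Treatment and control groups will be compared using the Fisher's exact test". I-QoL, 24-hour pad weight and pad use form the family intended to support later labelling and marketing. The Hochberg procedure "with a total alpha of 0.05 will be used to address multiple endpoint related multiplicity problems", and the family is analysed only if the primary efficacy endpoint is met. Sidedness is not stated for I-QoL.

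**Analyses of the score itself (Section 9.5).** These sit outside the three formal tests. One is a t-test on the score, described as paired but meant to detect a difference between the groups. The other is an ANCOVA with baseline as covariate, listed as post hoc, although the plan names its advantage of accounting for variation in baseline.

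**What is not given.** There is no I-QoL standard deviation, expected difference, expected sham change, responder rate or power. The calculations in Section 9.1 concern the primary endpoint only.

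**The concern.** A score with 88 points of range is reduced to yes or no before the arms are compared. A woman who gains 3 points counts the same as one who gains 40, and one who gains 2 the same as one who worsens. With 20 control subjects there is little information to spare, and the comparison that uses the whole score is not the one on which a claim could rest.

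The effect can also reach the other two tests. Under Hochberg with three tests and total alpha 0.05, all three succeed if the largest p-value is at most 0.05. If it is not, the next is judged at 0.05/2 = 0.025, and then the smallest at 0.05/3 = 0.0167. An I-QoL p-value that is large only because the test is weak therefore tightens the bar for pad weight and pad use.

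The informal alternative does not fill the gap as written. A paired t-test works on differences within the same women, and it cannot compare two independent arms.

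**Working it through.** **1. The plan's own figures.** Section 9.1 states: "Each of these calculations target 80% power and assume an alpha of 2.5" percent, with "a 2:1 treatment to control randomization ratio, and a single-tailed test". The unpooled two-proportion formula for 2:1 allocation is

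n(active) = (1.960 + 0.842)² × [p1(1−p1) + 2·p0(1−p0)] / (p1−p0)²

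- 48% vs 13%: 7.85 × (0.2496 + 0.2262)/0.1225 = 30.5, so 31.
- 62% vs 13%: 7.85 × (0.2356 + 0.2262)/0.2401 = 15.1, so 16.
- 71% vs 15%: 7.85 × (0.2059 + 0.2550)/0.3136 = 11.5, so 12.

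All three agree with the plan. The one-tailed Fisher p-value for 24/40 vs 5/20 is 0.0105, the plan's 0.01. None of these figures concerns I-QoL.

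**2. What the cut-off means.** The range is 110 − 22 = 88. A sum of whole numbers cannot rise by exactly 2.5, so the rule acts as a rise of 3 or more. The cut-off is 2.5/88 = 2.8% of the range.

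**3. Method for power.** From the plan: 40 and 20 subjects. Assumed: normal change with standard deviation SD in both arms, sham mean change m, arm difference d, one-sided 0.025. A rounded change of at least 3 corresponds to a continuous change of at least 2.5, so

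- sham responder rate p0 = Φ((m − 2.5)/SD)
- active responder rate p1 = Φ((m + d − 2.5)/SD)

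Fisher power is the exact sum over all outcomes of the two binomials. The score test is a two-sample t-test on 58 degrees of freedom with noncentrality (d/SD) × √(40·20/60) = 3.65 × d/SD.

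**4. One case in full.** Take SD 10, m = 3, d = 8. Then p0 = Φ(0.05) = 52% and p1 = Φ(0.85) = 80%. Fisher power is 50%. The noncentrality is 3.65 × 0.8 = 2.92, and t-test power is 82%. The loss is 32 points.

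**5. Range for SD 8-16 and sham change 0-4.**

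| Effect | Fisher on responders | Two-sample score test | Loss (points) |
|---|---|---|---|
| 0.8 SD | 48-52% | 82% | 30-34 |
| 1.0 SD | 66-73% | 95% | 22-29 |
| 1.5 SD | 91-97% | nearly 100% | about 3-9 |

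**6. Wider grid (SD 8-20, sham change 0-8, difference 5-15 points).**

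| SD | Sham change | Difference | Fisher | t-test |
|---|---|---|---|---|
| 8 | 8 | 8 | 44% | 95% |
| 12 | 3 | 10 | 53% | 85% |
| 15 | 0 | 10 | 37% | 67% |
| 10 | 0 | 15 | 97% | 100% |
| 20 | 3 | 5 | 6% | 14% |

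Over the whole grid the loss is 0 to 51 points. Where the t-test has 80-95% power it is 22 to 51.

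**7. Split or cut-off?** With SD 10 and d = 8 the t-test has 82% power. Fisher at its best possible cut-off reaches 52%. At the plan's cut-off it reaches 52%, 50%, 47% and 38% for sham changes of 0, 3, 5 and 8. So 82 − 52 = 30 points go with the responder comparison itself (the split together with the conservatism of the exact test, not separated here). The value 2.5 adds 0, 2, 5 and 14 points.

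**8. ANCOVA.** In simulation at 0.8 SD (2,000 trials per setting), ANCOVA had 80-82% power when baseline and change were uncorrelated and 86-88% at a correlation of −0.4. It therefore performs about as well as the t-test or better.

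**The case against.** The best defence is that the threshold is attributed to regulatory guidance, that a responder proportion is easy to interpret, and that responder-plus-Fisher matches the primary and pad-weight tests. All of that supports reporting the proportion. It does not require that proportion to be the formal comparison. Whether the guidance defines its 2.5 points on this raw sum cannot be checked from the documents.

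Two further points stand in part. One-sided 0.025 is my assumption. At one-sided 0.05, with 0.8 SD and no sham change, Fisher has 64-65% power and the t-test 89%, so the gap narrows but remains. If the effect is very large, either test succeeds.

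A reader might infer more than the documents support:

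- **That the 2.5-point cut-off costs a fixed 30 points of power.** The size depends on unstated inputs, and step 7 shows that the cut-off itself is a minor cause unless sham improvement is large.
- **That about 4 in 10 unchanged women would count as responders.** With no true change the proportion is 11% at a noise SD of 2, 27% at 4, 38% at 8 and 43% at 15. No such SD is given. Noise of this kind affects both arms, and the Fisher test stays valid.
- **That skipped items corrupt the result.** No rule for blank items is given, but nothing says that a blank scores zero. Section 5.5 requires pre- and post-study requirements to be completed for compliance, and Section 10.5 has source documents verified as complete. Even with blanks scored zero, assumed skip rates of 0.5-1% change responder status in about 1.4-5.3% of women and move a group's rate by less than 1 percentage point.

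**Conclusion.** The point holds as a loss of efficiency in a formal secondary test. Under the assumptions in step 5 the loss is 30-34 points of power at 0.8 SD, 22-29 at 1.0 SD and about 3-9 at 1.5 SD. It spans 0 to 51 over the wider grid. These figures rest on normal change with equal spread in the two arms, the planned 40 and 20 subjects, and one-sided 0.025. The documents fix only the arm sizes. The direction is consistent across the settings examined, and the loss is small only where the effect is so large or so small that the choice of test hardly matters.

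The cause is mainly the responder comparison, not the number 2.5. No bias and no inflation of type I error is shown. Because I-QoL is tested only after the primary endpoint is met, the primary conclusion does not depend on it.

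**What to change.** In Section 9.5:

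1. Make the formal I-QoL test in the Hochberg family a between-arm ANCOVA of the post-study score on arm and baseline score, and state its sidedness and alpha.
2. Report the proportion rising by the 2.5-point cut-off as descriptive, with the note that this means at least 3 on the whole-number sum.
3. Replace the paired t-test for I-QoL with a two-sample comparison, or remove it as superseded by the ANCOVA.

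A prorating rule for skipped items, with a minimum number answered, may be added to Section 5.3 as housekeeping. It is not the basis of this point.

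The cost is wording only: the ANCOVA uses data already collected and needs no extra subjects. The change should be made before any I-QoL data are seen by arm. The one real downside is that the formal claim becomes a mean difference in score and not a percentage of responders.

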### 1.3 Design and Outcomes

This is a randomized controlled study in which subjects are assigned to either a treatment group or a control (sham) group. Pre- and post-study outcome measures evaluate the change in incontinence episodes on women with mild-moderate stress urinary incontinence.

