#### **1.5** Sample Size and Population

The population includes women ages 21-75 with mild-moderate stress urinary incontinence. The active and control groups will be enrolled in a 2:1 ratio, totaling 40 and 20 subjects respectively.

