## 9.2 Randomization

A subject is assigned to the active or control group upon returning her informed consent documentation. Assignment is based on pre-set randomization of small groupings. For example, a card drawn from a deck of nine cards, wherein each card is indicated as either active or control according to a 2:1 ratio (i.e. 6 cards are identified as active and 3 card as control). After a card has been drawn it is removed from the deck. After the ninth subject is assigned to the group corresponding to the ninth card, the nine card deck is re-shuffled and a card is drawn for the tenth subject. This process continues until enrollment is complete. Means equivalent to a card draw may alternately be used.

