### 9.5 Data Analyses

Analysis of the **primary efficacy endpoint** will proceed as follows. Each adherent subject's Daily Log will be used to determine the average number of SUI episodes per day for the baseline and  $12^{th}$  weeks (see 5.5 regarding subject adherence). To accommodate the likelihood that some subjects will omit log data, the "weeks" referred to in the baseline and 12th week assessments refer to the first and last 5 entries in the Daily Log. The percent reduction in SUI episodes is then calculated by subtracting the final week average from the baseline average, dividing the difference by the baseline average, and multiplying by 100. Subjects with a percent reduction of  $\geq$ 50% are considered responders. The number of responders from each group is then compared using a one-tailed Fisher's exact test for groups of unequal size, and p $\leq$ 0.025. For example, if 24 of 40 subjects (60%) from the active group responded and 5 of 20 (25%) from the control group responded, the active treatment would be considered effective (p=0.01).

SUI episodes per day data can additionally be characterized simply in terms of percent reduction (independent of whether it reaches a 50% level of clinical significance) and the treatment groups analyzed using a 2 sample t-test with unequal group sizes. This approach is commonly reported in the literature. This value may additionally be reported but is not intended for use in determining whether the study met its endpoint. This use of a secondary analysis method on a single endpoint after success of the primary analysis method is generally understood to not inflate the Type 1 error rate, so no multiplicity adjustments are necessary.

Also note that confidence intervals and associated effect size calculations may also be made on the same data, but no multiplicity adjustments are warranted. Similarly, the data may be additionally analyzed using intent-to-treat criteria instead of with per-protocol criteria as defined in 5.5.

Regarding **secondary outcome measures**, three tests are prospectively defined with the intent of using the results to support future product labeling and marketing. The Hochberg procedure

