In addition to characterizing outcome measures as achieving a clinically meaningful response (e.g. ≥50% change) or as change scores (i.e. delta values), post hoc analyses may investigate outcome measures using analysis of covariance (ANCOVA), wherein baseline values are modeled as covariates, which has the advantage of accounting for variation in the magnitude of the baseline. Additional post hoc ANCOVA may be performed with covariates including age, type of incontinence, BMI or other potentially relevant variables.

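### Section 9.5 names a paired t-test to compare two independent arms on pad weight, I-QoL and pad use; the test does not fit the question

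*Combined protocol and SAP*

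**What the plan says.** After the three formal secondary tests, section 9.5 lists further analyses, introduced as "Other analyses that may be made but which are not prospectively included within the group of three formal secondary outcome measures". The first item states "Alternate analysis methods for the 24h Pad Weight, I-QoL and Pad Use test will be performed", and then that the mass, score or number data can be "analyzed using a paired sample ttest to determine whether there is a mean difference between the groups".

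The design sections describe parallel arms:

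- Section 1.3: "This is a randomized controlled study in which subjects are assigned to either a treatment group or a control (sham) group".
- Section 1.5: "The active and control groups will be enrolled in a 2:1 ratio, totaling 40 and 20 subjects respectively".
- Section 9.2: "A subject is assigned to the active or control group upon returning her informed consent documentation". The mechanism is a draw from a shuffled deck of nine cards, six active and three control.

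Elsewhere, section 9.5 handles similar continuous comparisons differently. For percent reduction in SUI episodes it has "the treatment groups analyzed using a 2 sample t-test with unequal group sizes". Its closing paragraph mentions change scores and, as a post hoc option, ANCOVA with the baseline value as covariate.

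**The concern.** A paired t-test needs each observation in one set to have a natural partner in the other. In this trial no active subject is linked to a control subject, so the named test cannot deliver the between-group comparison that the same sentence gives as its purpose.

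Two things could follow. The analyst may replace the test with one of his or her own choosing, in which case the choice is no longer prespecified. Or the analyst may run paired tests before and after within each arm and read the pair of results as evidence about the device. That second course would credit the device with improvement that both arms share. It would also favour the active arm, because an arm of 40 reaches significance more easily than an arm of 20.

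**Working it through.** The plan attaches no power, sample size or p-value to this test, so there is no stated figure to reproduce. The check is of test against question, followed by an illustration.

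**1. Can the named test be run between arms?** The planned arms are 40 and 20 (section 1.5). Blocks of six active and three control assignments (section 9.2) balance numbers but form no one-to-one pairs. A paired calculation on 40 values against 20 values fails because the lengths do not match. Even with equal numbers, the result would depend on an arbitrary ordering of subjects.

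**2. Is there another pairing that answers the question?**

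| Possible pairing | Source | What a paired test would address |
|---|---|---|
| Before and after within a subject, by arm | Section 5.3: pre- and post-study I-QoL and pad test; Daily Log for pads | Change over time in that arm (df = 40 − 1 = 39, or 20 − 1 = 19) |
| Control subjects who later take the optional 6 weeks of active treatment | Section 4.4 | Controls only; optional, and not set out as a comparison |

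Neither compares the randomized arms. In the three formal tests immediately above, *groups* means treatment and control, so the word cannot easily be read as meaning the two time points.

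**3. What does a fitting test look like?** A two-sample t-test on change from baseline is available at these sizes. In the pooled form:

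- df = 40 + 20 − 2 = 58
- SE = SD × √(1/40 + 1/20) = SD × √0.075 = 0.274 SD

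**4. Illustration only: within-arm tests read side by side.** The plan does not state this rule. Assume normal change scores, equal SDs, the same true change in both arms (so no device effect), and d = common change ÷ SD of change. Each arm is tested by a paired t-test with upper tail 0.025, and the power comes from the noncentral t distribution. Then

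P(active significant, control not) = P(significant | n = 40) × [1 − P(significant | n = 20)]

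| d | Calculation | Result |
|---|---|---|
| 0 | 0.025 × (1 − 0.025) | 0.024 |
| 0.2 | 0.234 × (1 − 0.134) | 0.203 |
| 0.4 | 0.694 × (1 − 0.397) | 0.419 |
| 0.6 | 0.959 × (1 − 0.721) | 0.268 |
| 0.8 | same formula | 0.076 |
| 1.0 | same formula | 0.011 |

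The peak is 0.420 at d = 0.415. Simulation with 100,000 trials at each of these values of d gave 0.024, 0.204, 0.418, 0.266, 0.077 and 0.011. In the same simulated trials, a two-sided two-sample t-test on change at 0.05 rejected in 0.049 to 0.051 (unequal-variance form) and 0.048 to 0.051 (pooled form). The documents give no SD of change, so no value of d is favoured.

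**The case against.** The strongest reply is that this is a naming slip in optional text. The list is introduced as analyses that may be made, and the sentence itself says only that the data can be analyzed this way. Nothing formal depends on it. The authors evidently know the right tool, since the same section names a two-sample t-test for SUI episodes and mentions ANCOVA. *Paired* may loosely mean that each subject's pre/post difference is the quantity compared between arms, in which case only the name is wrong. And because a paired test cannot be run on 40 against 20, the literal reading would fail visibly and could not produce a misleading p-value.

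Most of this stands, and it is why the point is minor. The status wording is mixed, however: the same item also says that alternate methods will be performed. The two-sample test is specified only for SUI percent reduction, and the ANCOVA is optional and post hoc, so neither supplies the instruction for these three endpoints. A loose reading of *paired* does not make the printed test correct.

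It is also fair to say that the within-arm rates describe a decision rule that the plan never states. They show why a within-arm reading would be unsafe. They do not measure the error.

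**Conclusion.** The concern holds, as a minor specification error. Section 9.5 names a test that does not fit its stated purpose, and no other part of the document corrects it. The conclusion rests only on the arms being independent and unmatched, which sections 1.3, 1.5 and 9.2 make clear.

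There is no effect on the primary Fisher test, the sample size, alpha or the three Hochberg-controlled secondary tests. As a mismatch of test and question, the error carries no numerical size. The illustrative range of about 1% to 42% applies only to a within-arm reading under the assumptions listed with it, and no value in that range is favoured.

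**What to change.** In the first item of the additional analyses in section 9.5, replace the paired test with one of two methods, stated in advance for all three endpoints:

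- a two-sample t-test comparing each subject's change from baseline between arms; or
- ANCOVA of the post-study value on arm with the baseline value as covariate, which the closing paragraph of 9.5 at present offers only post hoc.

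If the t-test is chosen, state whether variances are pooled. The unequal-variance form is a reasonable choice, but the wording of 9.5 for SUI episodes refers to unequal group sizes and does not specify it. If within-arm paired tests are reported as well, label them descriptive.

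The cost is one sentence, with no new data and no change to sample size or alpha.
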